5.1 Pre-treatment Criteria

5.1.1 The following evaluations must be performed within four weeks prior to ECP for all patients

- Medical history and documentation of the rationale for treatment of the patient's disease (including steroid dose).
- Physical examination, including vital signs, weight, performance status.
- cGVHD assessment (Section 10.1)
- Pregnancy test for women of childbearing potential.
- Hematology: Complete blood count (CBC) with differential.
- Serum chemistries: glucose, BUN, creatinine, uric acid, total bilirubin, alkaline phosphatase, LDH, total protein, albumin, AST, ALT, and calcium.
- Thyroid function tests (TSH, T4, free T4).
- CMV viral load
- Quantitative serum immune globulins
- Immunology: plasma banking; and storage of additional mononuclear cells.

5.1.2 The following evaluations are required (except where indicated) within four weeks prior to ECP for patients with cGVHD involving specific organ systems

- Ocular examination with a Schirmer's test, for patients with ocular cGVHD (optional).
- Dermatologic assessment (\pm biopsy), for patients with cutaneous cGVHD.
- Oral examination (\pm biopsy), for patients with oral cGVHD (optional).

CONFIDENTIAL

This document is confidential. Do not disclose or use except as authorized.

Phase II ECP and IL-2 for chronic GVHD

Version 2.0; August 15, 2016

- Pulmonary function tests, for patients with pulmonary manifestations of cGVHD (within 4 weeks prior to treatment to 1 week after).
- Flexion assessment of affected joints, for individuals with contractures or musculoskeletal involvement related to cGVHD.

5.1.3 Evaluations during ECP and IL-2 treatment (End of Weeks 1, 2, 4, 6, 8, 9, 10, 12, 14), and off-study (End of Week 16)

- Medical history and clinical examination (including steroid dose, weeks 8 & 16).
- Drug diary review with member of study team (starting with IL-2 treatment).
- Toxicity assessment will be done on the same day as history and clinical examination.
- Hematology: CBC with differential.
- Serum chemistries: glucose, BUN, creatinine, uric acid, total bilirubin, alkaline phosphatase, LDH, total protein, albumin, AST, ALT, and calcium.
- CMV Viral load (or per institutional practice).
- Quantitative serum immune globulins (weeks 4, 8, 12, 16).
- Immunology: plasma banking; and storage of additional mononuclear cells (weeks 1, 2, 4, 6, 8, 9, 10, 12, 14, 16)
- Thyroid function tests (TSH, T4, free-T4) (week 16)

5.1.4 The following assessments are required (except where indicated) at end of week 8 and 16 of study (in addition to cGVHD symptom score) for patients with cGVHD involving specific organs:

- cGVHD assessment (Section 10.1)
- Ocular examination with a Schirmer's test, for patients with ocular cGVHD (optional).

CONFIDENTIAL

This document is confidential. Do not disclose or use except as authorized.

Phase II ECP and IL-2 for chronic GVHD

Version 2.0; August 15, 2016

- Dermatologic assessment (\pm biopsy), for patients with cutaneous cGVHD.
- Oral examination (\pm biopsy), for patients with oral cGVHD (optional).
- Pulmonary function tests, for patients with pulmonary manifestations of cGVHD.
- Flexion assessment of affected joints, for individuals with contractures or musculoskeletal involvement related to cGVHD.

5.2 Agent Administration

5.2.1 IL-2

Recombinant human IL-2 (Aldesleukin) (Proleukin®-Novartis Inc. & Prometheus Labs, Inc.) for this study is supplied free of charge by Prometheus Laboratories, Inc.

5.2.2 Clinical Trial Materials

Recombinant human IL-2 (Proleukin®) is supplied as a sterile, white to off-white, lyophilized cake in single-use vials containing 22 MIU of aldesleukin intended for intravenous (IV) administration. Store vials of lyophilized IL-2 in a refrigerator at 2-8°C (36-46°F). Do not use beyond the expiration date printed on the label.

5.2.3 Preparation, Handling, and Storage of Study Drug

Please refer to section 7.1 for detailed information in this regard.

5.2.4 Drug administration and dosage schedule

IL-2 may be self-administered by daily subcutaneous injection. Teaching will be provided before the first subcutaneous injection (see Appendix J for instructions for subcutaneous injection).

The pharmacist, or the primary pharmacy technician working under the supervision of the pharmacist, will prepare the drug under aseptic conditions. The amount (in IU) of drug to be administered will be determined based on body surface area (BSA). BSA is to be calculated using the DuBois formula. (Appendix B; section 17.2). The dose should be calculated based on body weight at screening, at a dose of 1 x

CONFIDENTIAL

This document is confidential. Do not disclose or use except as authorized.

Phase II ECP and IL-2 for chronic GVHD

Version 2.0; August 15, 2016

10^6 IU/m²/day. Subsequent dose modifications, if any, will be per the guidelines in section 6.2.

DO NOT ADMINISTER AS INTRAVENOUS PUSH OR BOLUS.

Premedications are not required prior to the first dose or later doses.

5.3 General Concomitant Medication and Supportive Care Guidelines

Antiviral, antifungal and antibacterial prophylaxis and monitoring should follow institutional practice for routine cGVHD management guidelines. These typically include: daily acyclovir (or equivalent) for HSV prophylaxis, bactrim (or equivalent) for PCP prophylaxis, IV gammaglobulin for hypo-gammaglobulinemia, and optional azole use for fungal prophylaxis in higher risk patients; as well as monitoring of CMV viral load, beta-glucan and galactomannan levels.

5.4 Duration of Therapy

Duration of therapy will be as per the schema outlined previously. In the absence of treatment delays due to adverse events, ECP plus IL-2 treatment may continue until one of the following criteria applies:

- The subject withdraws consent
- Non-compliance
- Administrative reasons
- Unacceptable adverse event
- Life threatening anaphylactic reaction to IL-2
- Other grade 4 toxic event (unless it is an asymptomatic correctable laboratory result, e.g. uric acid)
- Recurrent or non-resolving grade 3 toxic event
- Severe hematologic toxicity that persists or recurs (section 6.2).
- Life threatening infection on IL-2, at the discretion of the treating physician.
- Malignant relapse
- Clinical worsening of GVHD requiring the addition of a new immunosuppressive medication per the judgment of the treating physician. An increase in the corticosteroid dose will be considered evidence of worsening GVHD. Changes in other immunosuppressive medication doses to maintain a therapeutic level alone will not be criteria for removal from the trial.
- General or specific changes in the participant's condition render the participant unacceptable for further treatment in the opinion of the treating investigator.

CONFIDENTIAL

This document is confidential. Do not disclose or use except as authorized.

5.5 Duration of Follow Up

Participants will be followed for 1 year from the start of ECP plus IL-2 therapy or until death, whichever occurs first. Participants removed from study for unacceptable adverse events will be followed until resolution or stabilization of the adverse event. Participants will also be asked to allow for long-term follow up so that late toxicities, should they occur, may also be identified. Follow-up for participants benefiting on extended-duration therapy may continue beyond 1 year post start of IL-2.

Follow up will be at study center if patients live locally or with their local oncology providers if they live remotely. For patients living remotely, phone calls to their local oncology providers may be made on a 6 monthly basis.

5.6 Criteria for Removal from Study

Participants will be removed from study when any of the criteria listed in Section 5.4 applies. The reason for study removal and the date the participant was removed must be documented in the study-specific case report form (CRF). Alternative care options will be discussed with the participant.

In the event of unusual or life-threatening complications, participating investigators must immediately notify the Principal Investigator.

[name] DPhil,

[REDACTED]
[REDACTED]

CONFIDENTIAL

This document is confidential. Do not disclose or use except as authorized.

6. EXPECTED TOXICITIES AND DOSING DELAYS/DOSE MODIFICATIONS

Dose delays and modifications will be made using the following recommendations. Toxicity assessments will be done using the CTEP Version 4.0 of the NCI Common Terminology Criteria for Adverse Events (CTCAE) which is identified and located on the CTEP website at: http://ctep.cancer.gov/protocolDevelopment/electronic_applications/ctc.htm.

ECP is a standard-of-care therapy and its adverse events, for instance, hemorrhage from heparin exposure, cytopenias, and procedure intolerance (i.e. constitutional symptoms or cardiovascular instability) are rare.⁴⁵ Apheresis physicians will evaluate for procedure-related toxicities per the transfusion medicine SOP. ECP may also exacerbate underlying constitutional symptoms or cardiovascular instability, e.g. in the setting of mild dehydration, or suboptimally controlled hypertension. Such exacerbations are rare and transient and routinely managed by apheresis physicians per the transfusion medicine SOP.

If possible, symptoms should be managed symptomatically. In the case of toxicity, appropriate medical treatment should be used (including anti-emetics, anti-diarrheals, etc.).

All CTCAE grade 3 and higher adverse events experienced by participants will be collected, through the study and until the final week 16 study visit. Participants continuing to experience toxicity at the off study visit may be contacted for additional assessments until the toxicity has resolved or is deemed irreversible.

The dose modifications in section 6.2 are recommended but not mandatory for participants proceeding on indefinite extended-duration IL-2 at the end of the 16 week study.

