6.2 Dose Modifications/Delays

Toxicities are to be assessed according to the NCI Common Toxicity Criteria for Adverse Events (CTCAE), Version 4.0 (Appendix H; section 17.8)

- Anaphylaxis: Life threatening anaphylaxis related to IL-2 requires discontinuation of IL-2.
- Thrombotic microangiopathy: TMA during IL-2 therapy requires discontinuation of IL-2 if it is associated with CNS dysfunction, renal dysfunction requiring hemodialysis/CVVH, or need for hospitalization.
- CTC Grade 4 toxicity: Grade 4 non-hematologic toxicity related to IL-2 requires discontinuation of IL-2, unless it is an asymptomatic correctable lab test abnormality (e.g. uric acid).
- CTC Grade 3 toxicity: IL-2 will be withheld for Grade 3 non-hematologic toxicities related to IL-2, unless it is an asymptomatic and correctable lab test result abnormality (e.g. uric acid). If the toxicity resolves to grade 1 or below within 2 weeks, IL-2 can be restarted at 50% dose that will not be re-escalated. If the toxicity does not resolve in 2 weeks to grade 1 or below, or recurs to grade 3 or above after restarting IL-2, it will be discontinued. IL-2 may also be withheld for Grade 3 non-hematologic toxicities unrelated to IL-2 per physician discretion. If withheld, subsequent management is suggested per above guidelines.
- Expected non-hematologic toxicity: IL-2 can be withheld and/or restarted at 50% dose for less than grade 3 toxicity (local site reactions, persistent constitutional symptoms) depending on patient tolerability and the discretion of the treating physician.

CONFIDENTIAL

This document is confidential. Do not disclose or use except as authorized.

Phase II ECP and IL-2 for chronic GVHD

Version 2.0; August 15, 2016

- Severe hematologic toxicity: IL-2 will be withheld for severe declines in peripheral counts (ANC<500, Plts<10,000) not related to malignant disease relapse, infection or other etiologies. If counts improve (ANC>1000, Plts>20,000) within 2 weeks, IL-2 will be restarted at 50% dose and not re-escalated. If peripheral counts do not improve within 2 weeks, or drop again (ANC<500, Plts<10,000) after restarting IL-2, it will be discontinued.

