11.2 Procedures for AE and SAE Recording and Reporting

Reporting Participating investigators will assess the occurrence of AEs and SAEs at all participant evaluation time points during the study.

All CTC grade 3 or higher AEs and all SAEs whether reported by the participant, discovered during questioning, directly observed, or detected by physical examination, laboratory test or other means, will be recorded in the participant's medical record and on the appropriate study-specific case report forms.

The descriptions and grading scales found in the CTEP Version 4.0 of the NCI Common Terminology Criteria for Adverse Events (CTCAE) will be utilized for AE reporting. The CTEP Version 4.0 of the CTCAE is identified and located on the CTEP website at:

http://ctep.cancer.gov/protocolDevelopment/electronic_applications/ctc.htm.

All appropriate treatment areas should have access to a copy of the CTEP Version 4.0 of CTCAE.

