11.4 Reporting to the Study Sponsor

11.4.1 Serious Adverse Event Reporting

CONFIDENTIAL

This document is confidential. Do not disclose or use except as authorized.

Phase II ECP and IL-2 for chronic GVHD

[figure not shown]
Version 2.0; August 15, 2016

DF/HCC: All serious adverse events that occur after the initial dose of IL-2 study treatment, during treatment, or within 30 days of the last dose of treatment must be reported to the DF/HCC Overall Principal Investigator on the local institutional SAE form. This includes events meeting the criteria outlined in Section 11.1.2, as well as the following:

- Grade 2 (moderate) and Grade 3 (severe) events that are unexpected and at least possibly related/associated with the intervention.
- All Grade 4 (life-threatening or disabling) events that are unexpected and not specifically listed in the protocol as not requiring reporting. Grade 4 expected events related to stem cell transplantation that do not require reporting as SAEs include: neutropenia, neutropenic fever, thrombocytopenia, minor bleeding episodes (e.g. epistaxis), rashes, diarrhea, infections (e.g. pneumonia, line sepsis, cellulitis), VOD, TMA and GVHD as these are expected events related to stem cell transplantation.
- All Grade 5 (fatal) events while the participant is enrolled and actively participating in the trial OR when the event occurs within 30 days of the last study intervention.

Note: If the participant is in long term follow up, report the death at the time of continuing review.

Participating investigators must report each serious adverse event to the DF/HCC Overall Principal Investigator within 24 hours of learning of the occurrence. In the event that the participating investigator does not become aware of the serious adverse event immediately (e.g., participant sought treatment elsewhere), the participating investigator is to report the event within 24 business hours after learning of it and document the time of his or her first awareness of the adverse event. Report serious adverse events by telephone, email or facsimile to:

Within the following 24-48 hours, the participating investigator must provide follow-up information on the serious adverse event. Follow-up information should describe whether the event has resolved or continues, if and how the event was

CONFIDENTIAL

This document is confidential. Do not disclose or use except as authorized.

Phase II ECP and IL-2 for chronic GVHD

Version 2.0; August 15, 2016

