11.4.2 Non-Serious Adverse Event Reporting

Non-serious adverse events will be reported to the DF/HCC Overall Principal Investigator on the toxicity Case Report Forms.

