12.2 Safety Meetings

The DF/HCC Data and Safety Monitoring Committee (DSMC) will review and monitor toxicity and accrual data from this trial. The committee is composed of clinical specialists with experience in oncology and who have no direct relationship with the

CONFIDENTIAL

This document is confidential. Do not disclose or use except as authorized.

study. Information that raises any questions about participant safety will be addressed with the Principal Investigator and study team.

The DSMC will meet regularly to review toxicity and accrual data. Information to be provided to the committee may include: up-to-date participant accrual; current dose level information; DLT information; all grade 2 or higher unexpected adverse events that have been reported; summary of all deaths occurring within 30 days for Phase I or II protocols; for gene transfer protocols, summary of all deaths while being treated and during active follow-up; any response information; audit results, and a summary provided by the study team. Other information (e.g. scans, laboratory values) will be provided upon request.

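### Sections 6 and 11.2 conflict with 11.4.2 and 11.8 on which adverse events are recorded, so reasons for IL-2 holds or reductions below grade 3 can go unrecorded

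*Combined protocol and SAP*

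**What the plan says.** Two sections set a grade 3 threshold. Section 6, for the period up to the week 16 visit: "All CTCAE grade 3 and higher adverse events experienced by participants will be collected". Section 11.2, on what goes into the medical record and the CRF: "All CTC grade 3 or higher AEs and all SAEs whether reported by the participant".

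Two sections set no grade limit. Section 11.4.2: "Non-serious adverse events will be reported to the DF/HCC Overall Principal Investigator on the toxicity Case Report Forms". Section 11.8 asks that all adverse events, serious or not, be followed up, and that their presence and resolution be entered on the CRF with dates.

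Section 11.4.1 adds some lower-grade events to expedited reporting: "Grade 2 (moderate) and Grade 3 (severe) events that are unexpected and at least possibly related/associated with the intervention". Section 12.2 lists, among items that the DSMC may be given, "all grade 2 or higher unexpected adverse events that have been reported".

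Section 6.2, under expected non-hematologic toxicity, says "IL-2 can be withheld and/or restarted at 50% dose for less than grade 3 toxicity". It names injection-site reactions and lasting constitutional symptoms, and leaves the decision to tolerability and the treating physician.

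Toxicity of the combination is a secondary objective (Section 1.3) with no grade limit. Section 14.4 says only that secondary endpoints are reported descriptively.

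**The concern.** A site that follows 11.2 records grade 3+ events and SAEs. A site that follows 11.4.2 and 11.8 records every adverse event. Both could claim compliance, and the toxicity table would mean something different for each.

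The narrower reading loses one kind of event that bears on tolerability: a reaction below grade 3 that was bad enough for IL-2 to be withheld or restarted at half dose. Such a patient could appear in the toxicity summary with no event, while having received less IL-2 than planned. Section 6.1.1 says that most patients on daily low-dose IL-2 had injection-site reactions. It also describes interruption and lower-dose re-introduction for constitutional symptoms, without giving their grade. The situation is thus one that the protocol itself foresees.

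**Working it through.** This is mainly a comparison of texts.

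**Step 1. Scope of recording, section by section**

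| Section | Events covered | Grade limit |
|---|---|---|
| 6 | Adverse events collected to the week 16 visit | Grade 3+ |
| 11.2 | Medical record and CRF | Grade 3+, plus SAEs of any grade |
| 11.4.1 | Institutional SAE form | SAEs, plus grade 2–3 events if unexpected and at least possibly related (and further grade 4–5 provisions) |
| 11.4.2 | Toxicity CRFs | None stated |
| 11.8 | Follow-up and CRF entry with dates | None stated |

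Rows 1 and 2 cannot both describe the same CRF as rows 4 and 5.

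**Step 2. Trace one event**

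Take an expected, non-serious grade 2 injection-site reaction for which IL-2 is withheld and then restarted at half dose under 6.2.

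- *Sections 6 and 11.2:* below grade 3 and not an SAE, so no entry is required.
- *Section 11.4.1:* this section applies to events from the first IL-2 dose ("All serious adverse events that occur after the initial dose of IL-2 study treatment"), so timing does not exclude the reaction. Expectedness does. Section 11.1.3.1 treats an event as expected if it is on the adverse event list, and 6.1.1 lists both local reactions and constitutional symptoms. Unless its nature, intensity or frequency departs from that list (11.1.3.2), the reaction is expected and falls outside the grade 2 route.
- *Sections 11.4.2 and 11.8:* these would catch it, but they are the sections in conflict with 6 and 11.2.
- *Drug diary (Appendix J):* it asks for the date, whether the syringe contents were injected, and comments. No grade or reason is required. A half-dose syringe that was injected is still a yes.
- *Section 5.6:* this requires a CRF reason for removal from study, not for a hold or reduction.
- *Treatment Form (12.1.2):* it is listed, but its fields are not described.

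So no uncontested rule requires this event, its grade or its link to the dose change to be recorded. A grade 1 reaction follows the same path, since 11.4.1 does not reach grade 1 non-serious events.

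**Step 3. Does the gap touch the safety trigger?**

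Section 14.5 halts accrual for review if 3 or more of the first 10 patients starting IL-2 have grade 3+ treatment-related toxicity. With X ~ Binomial(10, p):

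P(X ≥ 3) = 1 − Σ(k = 0 to 2) C(10, k) p^k (1 − p)^(10 − k)

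| True rate p | Stated | Recomputed |
|---|---|---|
| 10% | 0.07 | 0.0702 |
| 30% | 0.62 | 0.6172 |
| 50% | 0.95 | 0.9453 |

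The stated figures reproduce. The trigger counts only grade 3+ events, so recording lower grades changes nothing in it.

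**Step 4. Size**

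The documents give no rate of IL-2 holds or reductions below grade 3. With 25 patients each one affected is 1/25 = 4 percentage points. For illustration only, 1, 3 or 5 such patients would be 4%, 12% or 20% of the trial. Under 6 and 11.2 the number whose reason must be recorded is zero, whatever the true number is.

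**The case against.** The strongest case on the other side is that the plan already collects what matters and the rest is a wording slip. Much of this stands.

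- A reader might infer that only grade 3+ events are collected. The protocol as a whole does not say so: 11.2 adds SAEs of any grade, and 11.4.2 and 11.8 have no grade limit. The defect is a conflict of scope.
- A reader might infer that the grade 2 events in 11.4.1 have nowhere to be recorded. They go on the institutional SAE form, and 11.2 puts SAEs on the CRF.
- A reader might infer that the DSMC's needs under 12.2 are unmet. That section is permissive and covers only events already reported, so it conflicts with nothing.
- A reader might infer that the endpoint misses the toxicity that limits IL-2. The dose-limiting toxicity in DFCI 07-083 was thrombotic microangiopathy, recorded as an SAE. The induration interruptions described in 6.1.1 were at grade 3. Both kinds are captured. Only the discretionary changes below grade 3 are at risk.
- A reader might infer that reduced exposure would be invisible. Missed doses show in the diary, which staff review, and the Treatment Form may show dose changes.

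It is also fair that a grade 3+ threshold is a legitimate choice for a small trial and matches the safety trigger. What the objection does not remove is that four sections disagree, and that none of the records described explicitly requires a graded reason for a hold or reduction below grade 3.

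**Conclusion.** The point holds as a conflict in the collection rule with one practical consequence. If Sections 6 and 11.2 are followed, the descriptive toxicity summary can omit the reasons for IL-2 holds and reductions below grade 3. Tolerability could then look somewhat better than it was, by an amount that the documents do not allow one to estimate.

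This rests on two assumptions: that sites work to 11.2 rather than 11.8, and that the undescribed Treatment Form does not already ask for a graded reason. If either is wrong, the loss shrinks, but the contradiction stays. Nothing here shows that the primary response endpoint is biased or that safety monitoring is weakened. The change is worth making because it is cheap and defines a secondary endpoint that is now open to two readings.

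**What to change.** Reconcile Sections 6, 11.2, 11.4.2 and 11.8 to one stated scope for the CRF:

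1. grade 3+ adverse events, as now;
2. all SAEs, as now;
3. the grade 2 events already reportable under 11.4.1;
4. events of any grade that lead to an IL-2 hold, reduction or stop, with grade and dates.

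All four sections need the edit. Changing 6 and 11.2 alone would leave the unrestricted wording in 11.4.2 and 11.8 in place. Full collection of grade 1–2 events is not needed.

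In 14.4, report the proportion of patients with IL-2 held, reduced or stopped for toxicity, by grade. A natural denominator is the set that Section 10 already calls evaluable for toxicity, those with at least one IL-2 dose.

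The cost is a few more CRF lines per patient and possibly a less favourable tolerability summary. No dosing rule, sample size or decision rule changes.
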